| Racial Categories | Not Hispanic or Latino | | Hispanic or Latino | | |
| | Female | Male | Female | Male | Total |
| American Indian/Alaska Native | 1 | 1 | 0 | 0 | 2 |
| Asian | 13 | 15 | 0 | 0 | 28 |
| Native Hawaiian or Other Pacific Islander | 1 | 1 | 0 | 0 | 2 |
| Black or African American | 20 | 22 | 0 | 0 | 42 |
| White | 123 | 141 | 17 | 19 | 300 |
| More Than One Race | 0 | 0 | 0 | 0 | 0 |
| Total | 158 | 180 | 17 | 19 | 374 |

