4.7 Criteria for Removal of Patient from Protocol Participation

- a. Patient completes 12 months of study participation.
- b. Patient does not receive at least one cycle of chemotherapy within the first 90 days after registration.
- c. The patient may withdraw from the study at any time for any reason. (Research staff should only submit the S1417CD Off Protocol Notice if the patient refuses both direct and indirect follow-up on the study. If the patient allows for indirect follow-up or is refusing to complete any further patient forms but will allow the site to follow them directly, do not submit the S1417CD Off Protocol Notice and continue to submit the site-completed forms at the time points required in Section 9.4b.)
- d. Patient death.

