6.0 CRITERIA FOR EVALUATION AND ENDPOINT ANALYSIS

- 6.1 Primary Endpoint
 - a. Major Financial Hardship: Defined as one or more of the following during the 12 month study period: debt accumulation of any amount, selling or refinancing home, ≥ 20% income decline, borrowing money of any amount from family/friends.
- 6.2 Secondary Endpoints
 - a. Treatment Non-Adherence: Defined as refusing treatment or skipping doses due to cost concerns (e.g., lack of coverage, high co-payment requirement)

- b. Health-related Quality of Life (HRQOL): As measured by the EORTC Quality of Life Questionnaire C30 (QLQ-C30) v. 3.0. (14) This is a well-validated questionnaire which includes 30 items assessing global quality-of-life, functioning in five domains (physical, role, cognitive, emotional social) and several items assessing specific symptoms (e.g. fatigue, trouble sleeping, pain). Importantly, the QLQ-C30 does include one item assessing the impact of medical treatment on finances. Questionnaire responses will be transformed into a linear score (0 to 100) using the EORTC scoring manual.
- c. Out-of-Pocket Expenses: Defined as total out-of-pocket direct medical (e.g., prescriptions, physician visits, deductibles) and non-medical (transportation, meals) expenses in the 3 months prior to each study visit.
- d. Credit History (TransUnion): Credit reports are obtained at baseline, 6 months, and when the patient goes off protocol and measure the following: non-mortgage amounts past due on credit cards and bankcards; non-mortgage credit card and bankcard balances; bankruptcies, liens, collections or repossessions.

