7.2 Secondary Objectives

Risk Factors for Financial Hardship

Sample size calculation will be driven by the key secondary objective of this study, which is to assess whether major financial hardship at one year differs by age (< 65 vs. \geq 65), race (white vs. non-white), marital status (married vs. unmarried), employment status (any employment vs. unemployed), and income (household income < \$50,000 / year vs. \geq \$50,000 / year). In particular, we hypothesize that financial hardships are more likely in patients who, at diagnosis, are younger, non-white, unmarried, unemployed, or have lower incomes.

With a series of 5 hypotheses to be tested, we account for multiple comparisons using a conservative Bonferroni alpha = 0.01 two-sided test for each comparison. Three years of accrual with one year of follow-up is anticipated. Based on a two-sample survival design accounting for the competing risk of death (40% deaths at 1 year [hazard rate of 0.51]), n=320 eligible, evaluable patients will give 90% power to detect an absolute difference of 20% (that is, 30% rate at year 1 in good performing group [hazard rate 0.356] vs. 50% in poor performing group [hazard rate of 0.693]) in the proportion of patients with major financial hardship, if a ratio of patients between two groups is 1:1. This corresponds to a hazard ratio of 1.95. Power drops to 83% if the ratio of patients in subgroups is 2:1.

The effect of age, race, marital status, employment status, and income on major financial hardship will be estimated using multivariable Cox regression. The regression will include the 5 covariates of interest plus insurance status, education, and gender. A sample size of 320 eligible patients ensures that the ratio of events to independent predictors will be at least 10:1. (22, 23)

Major Financial Hardship and HRQOL:

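### Section 7.2's 90% and 83% power need more than the 12 months of follow-up the protocol allows, and no power is given for the roughly 4:1 race split its own accrual table implies

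*Combined protocol and SAP*

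**What the plan says.** Section 7.2 (Risk Factors for Financial Hardship) states that "Sample size calculation will be driven by the key secondary objective of this study". That objective is five two-group comparisons, one of them "race (white vs. non-white"), each tested at a Bonferroni two-sided alpha of 0.01. The design allows for competing death (hazard 0.51) and contrasts year-1 hardship rates of 30% and 50% (hazards 0.356 and 0.693, HR 1.95). Power with 320 evaluable patients is 90% at 1:1, and "Power drops to 83% if the ratio of patients in subgroups is 2:1". No other ratio is considered, and neither the formula nor the larger group at 2:1 is named. On timing, 7.2 says: "Three years of accrual with one year of follow-up is anticipated".

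On direction, "we hypothesize that financial hardships are more likely in patients who, at diagnosis, are younger, non-white", so for race the smaller group is expected to have the higher hazard. The accrual table in section 2.0 has the row "White | 123 | 141 | 17 | 19 | 300" against a total of 374.

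Elsewhere each patient's observation stops at one year. The endpoint in 6.1 is "Defined as one or more of the following during the 12 month study period". The first removal criterion in 4.7 is "Patient completes 12 months of study participation". Section 4.9 requires nothing further after that, and the calendar in 5.0 ends at Month 12. Section 7.1 says that 1-year hardship will be estimated by cumulative incidence, with death as a competing risk.

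**The concern.** There are two separate gaps. First, the stated power appears to count hardship events after month 12, which the study will not collect. If so, every power figure in 7.2 is too high for the hazards it prints. Second, one of the five comparisons said to drive the sample size is expected at about twice the worst imbalance that 7.2 considers.

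What is at stake is how a non-significant result is read. A reader of a null race finding has only 90% and 83% to judge it by. At 83%, a true effect of the design size is missed about 1 time in 6. At 60%, it is missed about 4 times in 10.

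**Working it through.** **Inputs.** From 7.2: hazards 0.356 (low) and 0.693 (high), death 0.51, alpha 0.01 two-sided (z = 2.576), n = 320, ln HR = ln(0.693/0.356) = 0.666. From the table in 2.0: 374 - 300 = 74 non-white, and 300/74 = 4.05. Scaled to 320 this is 320 x 300/374 = 257 and 320 x 74/374 = 63, assuming that losses are proportional and that Hispanic white patients count as white.

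**Event probability**, with t = h + 0.51:
- 12 months: (h/t)(1 - exp(-t)). Low hazard: 0.411 x 0.579 = 0.238. High hazard: 0.576 x 0.700 = 0.403.
- 1-4 years (uniform 3-year accrual plus 1 year): (h/t)[1 - (exp(-t) - exp(-4t))/(3t)]. This gives 0.350 and 0.529.

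**Formula.** Power = Phi(ln HR / sqrt(1/d_low + 1/d_high) - 2.576), where d is the expected number of events in each group.

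**Reproducing the stated figures (1-4 years).**
- 1:1: events 55.9 and 84.7. 0.666/0.1723 - 2.576 = 1.289, power 90%.
- 2:1, higher hazard in the larger group: events 37.4 and 112.8. 0.666/0.1887 - 2.576 = 0.954, power 83%.
- 2:1, higher hazard in the smaller group: power 88.5%.

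So 90% and 83% are recovered, the latter with the larger group at the higher hazard, which is the opposite of race.

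**Same hazards, 12 months.**
- 1:1: events 38.1 and 64.5. 0.666/0.2043 - 2.576 = 0.684, power 75%.
- Race: events 61.2 and 25.4. 0.666/0.2360 - 2.576 = 0.246, power 60%.

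**Log-rank simulation** (death treated as censoring, no other dropout), beside the formula:

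| Split | 1-4 years: simulation (formula) | 12 months: simulation (formula) |
|---|---|---|
| 1:1 | 91% (90%) | 77% (75%) |
| 2:1, smaller group higher | 88% (88.5%) | 74% (74%) |
| 2:1, larger group higher | 85% (83%) | 68% (65%) |
| Race, 257:63 | 75% (76%) | 60% (60%) |

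With 10% dropout, race on 12 months is 58% by simulation. If the 36 Hispanic white patients (17 + 19) are coded non-white, the split is 264:110 (2.4:1) and race has about 86% on 1-4 years and 71-72% on 12 months.

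**Scale of the effect.** Ignoring death, 1 - exp(-0.356) = 30% and 1 - exp(-0.693) = 50%, a 20-point difference. With death competing, the proportions with hardship by 12 months are 23.8% and 40.3%, a difference of 16.5 points. Solving the 12-month formula for 30% and 50% gives hazards of about 0.471 and 0.951, HR 2.02 (ln HR = 0.703). Then:
- 1:1: events 48 and 80. 0.703/0.1826 - 2.576 = 1.28, power 90%; simulation about 91%.
- 2:1: simulation about 86-88%.
- Race: events 77.1 and 31.5. 0.703/0.2115 - 2.576 = 0.75, power 77%; simulation about 76%.

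**The case against.** The strongest defence is that the design may be sound on 12 months after all. If the target is read on the 7.1 scale, 30% vs 50% in cumulative incidence, 12 months gives about 91% at 1:1 and 86-88% at 2:1. This stands as a reason not to call the study underpowered. It does not rescue the text, because 7.2 prints 0.356, 0.693 and 1.95, and those are not the hazards of that target once death competes.

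It can also be said that the 1-4 year basis is inferred, since the accrual and follow-up sentence could mean one year per patient. That is true of the wording. But with the printed hazards, one year per patient gives about 77% at 1:1, not 90%.

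A reader might infer that the plan promises 83% for race and fails to deliver it. It does not: 83% is conditional on 2:1 and is assigned to no factor. The gap is that no power is given for the expected split.

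A reader might also take race power to be as low as 64% (1-4 years) or 46% (12 months), which the Schoenfeld approximation gives. Simulation gives 75% and 60%. The approximation is poor here, with a hazard ratio near 2 and the higher hazard in a small group, and it should not be relied on.

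Finally, objective 1.2a is worded as descriptive, and the race split depends on how ethnicity is coded. Both points limit the consequence. Under the alternative coding, race is not below 83% on 1-4 years, although it still is on 12 months at the printed hazards.

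**Conclusion.** The point holds as a minor one, in two parts. (1) At the printed hazards, the stated 90% and 83% do not fit the 12-month limit. Power is about 77% at 1:1 and 68-74% at 2:1, and this applies to all five factors. (2) At the split implied by the accrual table, race has about 75% on 1-4 years and 60% on 12 months, both below the lowest stated figure, and 7.2 does not say so.

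The tempting summary that a true 20-point difference in race would be missed 4 times in 10 is not supported. The 60% belongs to HR 1.95, which is 16.5 points in cumulative incidence. For 20 points on that scale race has about 76%, so about 1 in 4 would be missed.

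The figures assume exponential times, proportional losses, Hispanic white patients counted as white, no non-death dropout unless stated, and an unadjusted two-group comparison. Adjustment in the Cox model would lower them somewhat. For example, if the other seven covariates explained 10% of the variance in race (an assumption), the 12-month formula value would fall from 60% to 54%.

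**What to change.** Restate the power paragraph in 7.2 on 12-month follow-up, naming the method, which group is larger at 2:1, and the scale of the effect. Choose one of two targets:
- Keep 0.356 vs 0.693 (HR 1.95): about 77% at 1:1, 68-74% at 2:1 and 60% for race. Describe the effect as 23.8% vs 40.3% cumulative incidence, or say plainly that 30% vs 50% ignores death.
- Target 30% vs 50% cumulative incidence, in line with 7.1: correct the hazards to about 0.47 and 0.95 (HR about 2.02), giving about 91%, 86-88% and 76%.

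Either way, state that race is expected at about 4:1 (about 257 vs 63 evaluable), say how Hispanic white patients are classified, and note that a non-significant race result does not exclude the target difference. Use simulation, or a formula that agrees with it, and do not print Schoenfeld values. If observation beyond 12 months was intended, reconcile 7.2 with 4.7, 4.9, 5.0 and 6.1.

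The cost is a few sentences and, under the first option, less favourable stated power. Enrolment, data collection, the primary estimate and the Cox model stay as they are.

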4.0 INTERVENTION

4.1 Setting

This study will be conducted through all NCORP components and subcomponents. Enrollment will be limited to these sites in order to capture the financial impact of treatment in community clinical practices. The infrastructure for charity care and financial counseling may be different in NCORP sites compared with larger comprehensive cancer centers and the financial experiences of patients treated at NCORP sites may be more representative of the financial experiences of all mCRC patients in the United States.

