7.0 STATISTICAL CONSIDERATIONS

7.1 Primary Objective

The primary objective is to estimate the incidence of treatment-related major financial hardship (debt, selling/refinancing home, borrowing money from friends/family, ≥ 20% income decline) among evaluable patients with newly diagnosed metastatic colorectal cancer (mCRC) treated at NCORP sites.

Given serial measurements, the primary endpoint is time to first evidence of major financial hardship. Dropout due to death from mCRC will be a significant factor in this study. Recent randomized clinical trial data have reported 1-year survival of around 60% for this population. (19) Therefore death represents a substantial competing risk in the detection of financial hardship, which is accounted for in the study design. Both time to first evidence of major financial hardship and death are assumed to exhibit exponential decline. Dropout for reasons other than death (e.g. transferring care to another institution, withdrawal of consent) following enrollment in the study is estimated to be around 10% based on other studies in the literature. (20,21) Non-death related dropouts will be censored.

Based on preliminary data, we anticipate that 40% of patients will experience major financial hardship at some point in the first year after diagnosis. Estimates of major financial hardship at 1 year will be derived using cumulative incidence to account for competing risks.

Under this scenario, a sample size of n=320 eligible, evaluable patients will allow us to estimate the confidence interval to within \pm 8% (based on the upper bound of the 95% confidence interval using an exact binomial in patients with complete follow-up), if the assumed incidence is at least 40%. Thus this sample size will allow us to estimate the confidence interval to within \pm 20% of the assumed incidence (the "relative accuracy"). The relative accuracy will improve with higher incidence as shown in the table below. This estimate is conservative as it is based on the assumption of no information from the 50% of patients estimated to drop out.

| Assumed incidence (p) | 95% confidence interval about p | Confidence range | Relative accuracy [(95% CI upper bound – p)/p] |
|-----------------------|---------------------------------|------------------|--|
| 20% | 14.1% - 27.0% | ± 7.0% | ± 35.2% |
| 30% | 23.0% - 37.7% | ± 7.7% | ± 25.8% |
| 40% | 32.3% - 48.0% | ± 8.0% | ± 20.1% |
| 50% | 42.0% - 58.0% | ± 8.0% | ± 16.0% |

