The feasibility of successfully accruing to a prospective-multi-site longitudinal cohort study assessing financial outcomes in patients with metastatic colorectal cancer (mCRC) undergoing treatment within the NCORP network will be examined. The total anticipated accrual time is 3 years. To be conducted in that timeframe, each of the NCORP components (we anticipate 25 NCORP components) will each need to enroll, on average, about 5 patients per year. Accrual will be monitored regularly. Given the open eligibility criteria, we hypothesize that enrollment will be feasible. However accrual will be assessed at 1.5 years after study activation. If monthly average accrual in quarters 5-6 after study registration is < 50% of projected accrual, efforts will be made to increase accrual over the succeeding 6 month period. If after 2 years, monthly accrual remains < 50% of projected accrual, study revision will be considered. In order to address the potential for selection bias, we will compare demographics (age, race, gender, etc.) of the final cohort to the typical patient population seen at the various practice sites.

The feasibility of incorporating a caregiver component to the study will also be examined. Caregiver participation is optional. The caregiver component will be considered feasible if the designated caregivers for > 50% of eligible patients complete and submit their baseline and at least one follow-up assessment. We will use means, medians, proportions to describe the participating caregiver population. Our analyses will be largely descriptive. We will look at the proportion of caregivers who experienced changes in employment and expenses (caregiver questionnaire items 11 and 13). We expect that caregivers of patients who experience financial hardship will be more likely to report financial burden. We will therefore investigate the association between patient-reported financial hardship and level of caregiver-reported financial burden. We will compare proportion of caregivers experiencing 'high financial burden' (≥ 3 on Likert scale) for patients who do vs. do not report major financial hardship using two-sample t tests. If our caregiver accrual is very poor (<20%), we will focus on describing the patient population rather than attempting to correlate caregiver and patient responses.

7.3 Other Secondary Endpoints:

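### The incidence interval and the Cox model take no account of the roughly 25 enrolling NCORP components: coverage falls below 95% if hardship clusters by component, and site can confound race or income if site risk and patient mix are related

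*Combined protocol and SAP*

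**What the plan says.** Section 4.1 places the study in the NCORP network ("This study will be conducted through all NCORP components and subcomponents") and makes one remark about institutions: "The infrastructure for charity care and financial counseling may be different in NCORP sites compared with larger comprehensive cancer centers". The Feasibility part of 7.2 gives the expected number of sites ("we anticipate 25 NCORP components") and says that they "will each need to enroll, on average, about 5 patients per year", over three years of accrual.

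For the primary objective, 7.1 says: "Estimates of major financial hardship at 1 year will be derived using cumulative incidence to account for competing risks". It names no variance method for that estimate. The planned precision is that "a sample size of n=320 eligible, evaluable patients will allow us to estimate the confidence interval" to within ±8 points, calculated "using an exact binomial in patients with complete follow-up". An exact binomial interval assumes independent patients.

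For the risk factors, 7.2 tests five of them at two-sided 0.01 each and specifies a multivariable Cox model: "The regression will include the 5 covariates of interest plus insurance status, education, and gender". The eight covariates are age, race, marital status, employment, income, insurance, education and gender.

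Neither section mentions a site term, stratum, frailty, design effect or robust variance. The only planned analysis that uses the sites is a comparison, under Feasibility, of the cohort's demographics with those of the practices' usual patients. It addresses selection bias and changes no interval or hazard ratio.

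**The concern.** Patients at one component share its charity care, its financial counselling and the local cost of living. If these influence hardship, two patients from the same component resemble each other more than two from different components. This has two separate consequences.

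- **Precision.** An incidence interval computed as if patients were independent is too narrow, and this is the trial's primary result.
- **Confounding.** If components with higher hardship also treat more non-white or lower-income patients, part of the site difference appears in the Cox model as a difference by race or income. Section 7.2 treats the risk-factor comparison as the key secondary objective, and section 2.0 intends the results to guide interventions. It therefore matters whether hardship follows the patient or the institution.

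**Working it through.** **1. The plan's own interval.** Section 7.1 counts no information from the 50% expected to drop out, so n = 0.5 × 320 = 160. The exact (Clopper-Pearson) 95% interval at 40% (64/160) is 32.3% to 48.0%, as tabulated. The other three rows also reproduce with n = 160 (14.1–27.0, 23.0–37.7, 42.0–58.0). There is no clustering term in the calculation.

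**2. Component size.** 374/25 = 15.0 enrolled (5 per year × 3 years); m = 320/25 = 12.8 evaluable.

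**3. Coverage of an interval that ignores site.** The intra-component correlation (ICC) is not in the documents, so a range is assumed. With equal sizes, DE = 1 + (m − 1) × ICC = 1 + 11.8 × ICC. With unequal sizes and an assumed coefficient of variation of 0.6, DE = 1 + (1.36 × 12.8 − 1) × ICC = 1 + 16.4 × ICC. Coverage = 2Φ(1.96/√DE) − 1. The half-width is the upper side of the exact interval at 40% with effective n = 320/DE.

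| ICC (assumed) | DE, equal | Coverage | DE, CV 0.6 | Coverage | Half-width, n = 320, equal sizes |
|---|---|---|---|---|---|
| 0 | 1.00 | 95% | 1.00 | 95% | 5.6 |
| 0.01 | 1.12 | 93.6% | 1.16 | 93.1% | 5.9 |
| 0.02 | 1.24 | 92.2% | 1.33 | 91.1% | 6.2 |
| 0.05 | 1.59 | 88.0% | 1.82 | 85.4% | 7.1 |

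With equal sizes the standard error is understated by 1 − 1/√DE, that is 5%, 10% and 21%.

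A simulation of the cumulative incidence itself (320 patients, 25 unequal components) gave coverage of 93%, 89% and 81% at ICCs of 0.013, 0.028 and 0.074 when site was ignored. A component-level variance with a t reference gave 93% to 95%, with almost no loss at ICC 0.

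**4. Reserve in the planned ±8 points.** Counting 160 of 320 patients is equivalent to allowing DE = 2. If all 320 contribute, ±8 holds up to ICC = 1/11.8 = 0.085 with equal sizes, or 1/16.4 = 0.061 at CV 0.6. The expected 10% censoring lowers this somewhat.

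**5. Standard errors in the Cox model.** For a covariate with its own within-component correlation, DE ≈ 1 + 11.8 × ICC(outcome) × ICC(covariate). With outcome ICC 0.01 to 0.05 and covariate ICC 0.1 to 0.3, DE is 1.01 to 1.18. The true level of a nominal 0.01 test, 2[1 − Φ(2.576/√DE)], is then 0.010 to 0.018.

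**6. Confounding in the Cox model.** The simulations used 320 patients, 25 components, mean hardship hazard 0.51 (40% at one year), death hazard 0.51, censoring at 12 months, race as the only covariate and no true race effect. The correlation between site risk and non-white share was set at 0.5. Four sets of runs differed in the assumed share of non-white patients and its spread over sites.

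| Runs per setting | Site log-hazard SD 0.3: HR, rejection at 1% | SD 0.5: HR, rejection at 1% |
|---|---|---|
| 1000 | 1.15, 4.9% | 1.22, 9.6% |
| 400 | 1.12, 3.3% | 1.21, 6.5% |
| 600 | 1.10, 2.0% | 1.19, 6.7% |
| 2000 (20% non-white) | not recorded, 3.7% | not recorded, 6.3% |

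SDs of 0.3 and 0.5 correspond to an ICC of about 0.03 and 0.07, so the upper setting lies beyond the range in step 3. With no correlation, rejection stays near 1% (1.0% to 1.5%). At correlation 0.2 and SD 0.3, the last set gave 1.0%. A component-stratified Cox model gave HR about 1.0 and about 1% rejection. A cluster-robust variance on the unstratified model did not help: 4.2% and 7.4% in the last set, and 2.3% with no site effect at all, because 25 clusters are few.

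**7. Price of stratifying.** Expected events by 12 months are 320 × 0.5 × (1 − e^(−1.02)) = 102, about 4 per component. The accrual table in section 2.0 has 74/374 = 20% non-white, or 2 to 3 per component. With the plan's HR of 1.95 and 12 months of follow-up, simulated power for race was 69% unstratified and 51% stratified; a second simulation gave 63% and 47%. Adding 24 site indicators instead would mean 102/32 = 3.2 events per term, against the 10:1 rule in 7.2.

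**The case against.** Several points against the concern stand.

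- The documents give no ICC, no between-component variation in hardship, and no spread of race or income over sites. A reader might infer from 4.1 that NCORP sites differ among themselves. That section contrasts NCORP sites with larger cancer centers and does not say so. Variation within the network is plausible, but it is an inference.
- Section 7.1 names no variance method. That the reported interval will ignore site is read from the planning calculation and from silence.
- A reader might infer that the promised ±8 points fails. With the reserve in step 4 it does not, for the ICCs assumed here. But the reserve protects only the planned width. An interval computed from all patients and ignoring site would still under-cover.
- A reader might infer that the 0.01 level is not held and that the race and income hazard ratios are biased. This needs a link between site risk and patient mix that the documents do not report. The simulations are also race-only; the planned adjustment for income, employment, insurance and education could absorb part of such a link.
- Section 1.2 aims to describe associations. If patients' circumstances affect where they are treated, site lies partly on the pathway, and a stratified model answers a different, within-site question. Together with the loss of power, this is a good reason not to make it primary.

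None of this supplies the missing variance method in 7.1 or a check for site in 7.2.

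**Conclusion.** The concern holds in conditional form. Neither the planned incidence interval nor the Cox model accounts for component, and nothing else in the documents repairs this.

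For the incidence, coverage falls below 95% whenever the ICC is positive: to about 94% to 88% for assumed ICCs of 0.01 to 0.05 with equal sizes, and lower with unequal ones. The documents do not support stating under-coverage as a fact, because they do not give the ICC.

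For race and income, the inflation of standard errors is minor. Confounding is possible only if site risk and patient mix are related. Under the assumptions of step 6, it gives about 2% to 10% rejection at nominal 1% and a spurious HR of about 1.1 to 1.2. A claim that these tests have in fact lost their level goes beyond the evidence.

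**What to change.** - **Section 7.1:** state that the confidence interval for the cumulative incidence uses a component-level jackknife, bootstrap or robust variance with a small-cluster correction, namely a t reference with the number of components minus 1 degrees of freedom (24 if there are 25). Report the observed ICC.
- **Section 7.2:** keep the planned Cox model as primary. Pre-specify, as a sensitivity analysis reported beside it, the same model stratified by component, with small components pooled. Say that it estimates a within-site association and loses appreciable power. A cluster-robust variance alone is not a substitute, since it leaves confounding in place.
- State how institutions are grouped into components, since subcomponents also enrol.

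The institution is already recorded at registration (section 8.3), so no new data are needed. The cost is a few lines of text, a somewhat wider incidence interval and a little extra analysis.
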